## 4.3 Assessments

Assessment results will be recorded in the eCRF, as applicable.

### 4.3.1 Medical and surgical history

A verbal medical and surgical history will be collected from the participant/legal guardian as part of admission procedures and recorded as historical data in the source notes and eCRF. Medical history will not be verified by referring to existing participant notes or by contacting the participant's General Practitioner, for example. Due to the acute nature of this protocol in an ED setting, the scope of the exclusion criteria, the short duration of the participant within the study and the short acting nature of the IMP, verification of medical history is not reasonably practical.

### 4.3.2 Pain intensity assessments

The pain resulting from injury causing the emergency visit will be quantified. The participant will be introduced to the age-appropriate pain scale and overall pain will be assessed, with no distinction made between spontaneous pain and any procedural pain.

Immediately prior to administration of the IMP (baseline), the pain intensity will be rated using the applicable tool (see below). Subsequent pain assessments will be performed at 10, 15, 20, 30, 45, and 60 min post IMP administration. If a second dose of IMP is administered after 10-15 min, the pain assessment schedule will be reset, and pain will be measured at 10, 15, 20, 30, 45, and 60 min after the second dose of IMP, or until additional analgesics or procedures needs to be initiated.

Unscheduled pain intensity scores will be measured and recorded during any potentially painful intervention (e.g. during the application of a plaster cast for a fracture), prior to rescue medication or prior to premature study withdrawal.

Age-appropriate pain intensity assessment tools will be used:

**Age ≥9 years:** The Numerical Rating Scale (NRS) will be used. The NRS scales consists of a Likert scale, anchored with numbers 0-10, with 0 marked "No pain" and the right end (10) marked "Worst pain imaginable". The patient will state the number representing their current level of pain, and the study staff will circle the applicable number on the CRF page (see [Appendix A](#)).

**Age ≥5 to <9 years:** The visual analogue scale modified with six faces developed by Wong-Baker (Wong-Baker FACES pain rating scale) will be used. Numerical values (0, 2, 4, 6, 8, 10) are listed for each face (Wong et al, 2001, see [Appendix B](#)).

**Age 1 to <5 years:** The study investigator will provide an assessment of pain, using the FLACC scale (Merkel et al, 1997, see [Appendix C](#)).

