Statistical Methods	
General principles The primary objective of this study is to investigate the safety, tolerability and analgesic effects of CT001 in pediatric participants when used in an acute care setting.
 
Data will be summarised using descriptive statistics. For continuous endpoints, the descriptive statistics include number of subjects, mean, median, standard deviation, standard error, lower and upper quartiles, minimum, and maximum. For categorical endpoints, frequency, and percentage will be given. Figures showing population distributions, such as box plots and histograms, will be reported for all applicable endpoints. The method of handling missing data for efficacy endpoints will be described for each set of endpoints. Missing data will not be imputed for safety endpoints.
 
Sample size estimation So far, data from 375 children on IN sufentanil/ketamine show a safe and tolerable combination (data from PDC 01-0201, PDC 01-0203 and PDC 01-0206). Thus, from a safety perspective it is expected that 150 patients will be sufficient to capture and confirm the adverse event profile of the IMP.
 
A formal sample size calculation was made for the primary efficacy endpoint on the basis of expecting a responder rate of 60%. A previous study reported a responder rate of 71.6 %, defined as pain intensity <math>\leq 3</math> at 30 min post IMP (16). With a sample of 113 patients, a one-sample one-sided proportion design would provide at least 80% power to show that the responder rate is more than to 60%, with a significance level of 5%. Accounting for an approximate 25% dropout rate the resulting sample size is 150.
 
Study populations The full analysis set (FAS) will consist of all patients who received at least one dose of study treatment (CT001). The FAS follows the intention-to-treat (ITT) principle, i.e. patients will be analysed regardless of whether treatment was received as planned. The FAS will be used for all analyses of primary and secondary safety and efficacy objectives.
 
The FAS will be used to tabulate demographic data, baseline disease characteristics, and subject disposition.
 
Statistical analysis of the primary endpoints The primary objective of the study will be evaluated using the FAS population. Data will further be evaluated by age group.
 
Descriptive statistics will be used for safety variables. Safety variables of special interest consist of vital signs, respiratory rate, pulse rate, oxygen saturation (SpO2), heart rate as well as sedation.
 
Clinically significant out-of-range values and clinically significant relevant changes of values will be described descriptive statistics, number of subjects, number of events.
 
Adverse events will be coded according to the MedDRA dictionary. The frequencies of adverse events will be tabulated by body system and "preferred term".

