### Part 2; Baseline and IMP treatment (Day 1)

The baseline assessment will include a repeat pain score, sedation score, and measurement of the participant's vital signs (respiratory rate, pulse rate, oxygen saturation) if not already undertaken at

the routine triage assessment. Once the pre-treatment assessments are performed the IMP will be administered.

After administration of IMP, pain scores will be assessed at the following approximate intervals (10, 15, 20, 30, 45, 60 min post IMP), as specified in the Study Assessment Chart (Table 1). The actual timepoints for pain assessment relative to IMP administration will be recorded in the eCRF.

Unscheduled pain intensity scores will be measured and documented during any potentially painful intervention (e.g. during the application of a plaster cast for a fracture), prior to rescue medication or prior to premature study withdrawal.

Where pain relief at 10-15 min after the first IMP administration is insufficient (for example, a pain score >4/10 on NRS, or at the discretion of the treating investigator), a second IMP dose of similar strength and dose can be administered to the participant. In the case of insufficient pain relief after two doses of IMP, additional analgesic medication may be administered at the discretion of the treating investigator, in accordance with standard local practice. The medication, dose and time of administration will be recorded in the eCRF.

After administration of IMP, level of sedation, vital signs (pulse rate, peripheral oxygen saturation, respiratory rate), nasal tolerability and spontaneously reported adverse events will be assessed.

Pain scores and safety assessments should continue for 60 min after the last dose of IMP, or until additional analgesic treatment or procedures need to be initiated. For further guidance on assessments at the treatment and post-treatment visit (Part 2), see Study Assessment Chart, Table 1.

Feasibility and treatment satisfaction in relation to the IMP and route of administration will be assessed prior to ED discharge.

Treatment satisfaction will be addressed by using the following standardized question: *“How satisfied are you with the study drug that you/your child received? Please think about how it helped their pain, how it was given, any side effects, and how quickly you/your child recovered”*. Respondents will answer using a 5-point Likert scale (very unsatisfied, unsatisfied, neutral, satisfied, very satisfied).

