**Part 3; Text/telephonic follow-up for safety (Day 2-7)**

On day 2-7 the parent/legal guardian (or patient if aged 16 to <18) will be contacted via text message (if possible), asking if the patient has experienced any side effects following discharge from the ED. If the reply is “yes” or the person does not respond to the text, the site investigator will attempt to contact them by phone to obtain further information about these adverse events. A total of 3 attempts will be made to make telephone contact. If all attempts are unsuccessful, the patient’s General Practitioner (GP) may be contacted for any relevant follow-up information. For further guidance on assessments, see Study Assessment Chart in Table 1.

Table 1: Study Assessment Chart

Visit Number and Name	1 Screening	2 Baseline and IMP Treatment	3 Follow-up (phone)
Study day	1	1	2-7
Study Activities			
Signed Informed Consent	X		
Allocation of participant ID	X		
Inclusion/Exclusion Criteria	X		
Type of injury*	X		
Demographics*	X		
Relevant Medical and surgical history*	X		
Recent and Concomitant medication* g)	X	X	X
Weight*	X		
Peripheral oxygen saturation*		X	
Pulse rate*		X	
Respiratory rate*		X	
Sedation score a)		X	
Pain intensity assessment* b)	X	X	
Administration of IMP c)		X	
Adverse events/ Serious adverse events d)		X	X
Nasal tolerability e)		X	
Feasibility and Treatment satisfaction questions f)		X	

\* if data from assessments performed prior to ICF signature are part of normal ED procedure they can be used in the study.

- a) Sedation will be assessed immediately after pain intensity assessments using the UMMS score at baseline and at 10, 15, 20, 30, 45 and 60 min post-IMP. If a second dose of IMP is needed the sedation score will be performed at the same time points relative to the second dose.
- b) Pain assessment will be performed using age-appropriate scales and they will be performed at screening, at baseline (before IMP administration), and at 10, 15, 20, 30, 45, 60 min post IMP. If a second dose of IMP is needed, the pain assessment timepoints will continue for 60 min after last IMP or until additional analgesics or procedures needs to be initiated. Unscheduled pain assessments should be done during any potentially painful intervention (e.g. during the application of a plaster cast for a fracture), prior to rescue medication or prior to premature study withdrawal.

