## 6 RESPONSE VARIABLES AND ENDPOINTS

### 6.1 Assessment of Efficacy

#### 6.1.1 Primary efficacy variable

To investigate the analgesic efficacy of IN CT001 in pediatric participants in the acute care setting experiencing pain of moderate to severe intensity.

- Analgesic efficacy will be assessed as changes in pain intensity from baseline using age relevant scoring instruments (FLACC score for ages  $\geq 1$  year to  $< 5$  years, the Wong-Baker faces scale from ages  $\geq 5$  years to  $< 9$  years, and the 0-10 Numerical Rating Scale (NRS) from ages 9 and above). The pain assessments will be made prior to the first IMP dose (baseline) and then at the following timepoints: at 10, 15, 20, 30, 45, 60 min post first IMP dose. The primary efficacy endpoints will be the responder rate i.e., the percentage of participants that has a pain intensity score at 4 or below at 15 min and at any timepoint during 30 min post IMP.

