## **Primary efficacy analysis**

The primary efficacy endpoint will be reported using descriptive statistics only. The analgesic effect will be assessed as the proportion of participants that has a reduction of pain intensity to a score of 4 or below at 15 min and within 30 minutes post IMP (relative to baseline). A 95% confidence interval for the proportion of the participants with a pain reduction of 4 or less within the first 30mins post IMP will be evaluated and reported for each age group and for all subjects.

The pain intensity score is measured using different scales for each of the three age groups:

- Numerical Rating Scale, a self-reported ordinal, categorical scale with values 0-10, interval 1 for subjects aged 9 and less than 18.
- Wong-Baker, a self-reported ordinal, categorical scale with values 0-10, interval 2 for subjects aged 5 and less than 9.
- FLACC, an ordinal, categorical scale with values 0-10, interval 1 for subjects aged 1 and less than 5. Pain intensity assessment for this age group to be conducted by the investigator.

Given that the pain intensity is measured using different scales for each of the three age groups, subgroup analyses stratified by measurement scale may be appropriate. Graphical representation of pain intensity scores measured within 30mins post IMP administration will be produced in the form of boxplots for each age category/assessment scale.

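### The 15-minute primary responder endpoint has no single clock: section 4.3.2 restarts the pain schedule at the second dose, section 6.1.1 times the scores from the first, and nothing secures a score near 15 minutes in children re-dosed before then

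*Combined protocol and SAP*

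**What the plan says.** **Schedule after a second dose.** Section 4.3.2: "If a second dose of IMP is administered after 10-15 min, the pain assessment schedule will be reset". The same six times (10, 15, 20, 30, 45 and 60 min) then run from the second dose. Table 1, note b, gives a duration and no starting point: "the pain assessment timepoints will continue for 60 min after last IMP".

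**Clock for the primary variable.** Section 6.1.1 schedules the scores "at the following timepoints: at 10, 15, 20, 30, 45, 60 min post first IMP dose". The endpoint sentence that follows names no dose: "pain intensity score at 4 or below at 15 min and at any timepoint during 30 min post IMP". Section 7.4.1 does not name one either: "reduction of pain intensity to a score of 4 or below at 15 min and within 30 minutes post IMP". The Protocol Outline is equally silent.

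**Who is re-dosed.** Section 4.2, Part 2, allows a second dose at 10-15 min for insufficient relief, with the example "a pain score >4/10 on NRS, or at the discretion of the treating investigator". The Protocol Outline equates insufficient relief with a score above 4 on the age-appropriate scale, subject to investigator discretion.

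**What is recorded.** Section 4.2 treats the assessment times as approximate and adds: "The actual timepoints for pain assessment relative to IMP administration will be recorded in the eCRF". Unscheduled scores are required around painful interventions, before rescue and before withdrawal. Re-dosing is not on that list.

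**Missing scores.** The Protocol Outline states: "The method of handling missing data for efficacy endpoints will be described for each set of endpoints". Section 7.4.1 gives no such method and section 7.3 rules out imputation. Section 7.2 places every child who received a dose in the FAS.

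**The concern.** The 15-minute responder rate is a primary efficacy endpoint, yet two sections start its clock at different doses. A site that follows 4.3.2 to the letter need not take a score at 15 min after the first dose in a child re-dosed before then. An analyst who follows 6.1.1 will look for exactly that score.

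The children concerned are not a random subset. The re-dosing example (above 4) is the complement of response (4 or below), so most of them were doing badly when the schedule restarted. What the endpoint measures, and which children have a value for it, would then depend on an unstated choice. Analysis rules can be added later. A score that was never taken cannot.

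**Working it through.** The plan gives no figure for this point. Its sample size (113, raised to 150) is not questioned here.

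**Step 1: scheduled scores on the first-dose clock.** Inputs: post-dose times 10, 15, 20, 30, 45 and 60 min (4.3.2); second dose at t = 10 to 15 min (4.2). Under the reset, the scores fall at 10 min (and at 15 min if t = 15, provided it is taken before re-dosing), then at t+10, t+15, t+20, t+30, t+45 and t+60.

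| Dose 2 at (min) | Scheduled scores, min after dose 1 | Score at 15 min? | The score 15 min after dose 2 falls at |
|---|---|---|---|
| 10 | 10, 20, 25, 30, 40, 55, 70 | no | 25 |
| 11 | 10, 21, 26, 31, 41, 56, 71 | no | 26 |
| 12 | 10, 22, 27, 32, 42, 57, 72 | no | 27 |
| 13 | 10, 23, 28, 33, 43, 58, 73 | no | 28 |
| 14 | 10, 24, 29, 34, 44, 59, 74 | no | 29 |
| 15 | 10, 15, 25, 30, 35, 45, 60, 75 | yes | 30 |

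For a second dose at 10-14 min, the nominal schedule is empty between 10 min and 20-24 min. A window of ±4 min around 15 (11 to 19 min) contains no scheduled score. A window of ±5 min contains the 10-min score, plus the 20-min score when t = 10.

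**Step 2: the last-dose reading.** Every re-dosed child then has a scheduled 15-min score. For t = 10-14 it falls 25-29 min after the first dose and follows two doses, while in other children it falls at 15 min after one.

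**Step 3: the within-30-min endpoint.** On the first-dose clock, the scores after dose 2 and by 30 min number three (t = 10) or two (t = 11 to 15). On the last-dose clock the window closes at t + 30 = 40 to 45 min after dose 1. It can be scored either way; only the window and its meaning change.

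**Step 4: effect on the 15-min rate, first-dose clock.** Nothing in the documents fixes the inputs, so all three are assumptions: f = share re-dosed before 15 min and left without a 15-min score; r = 15-min response rate in the others; s = share of the unscored who would have scored 4 or below.

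- All scored: r(1 − f) + s·f
- Unscored counted as non-responders: r(1 − f), low by f·s
- Unscored dropped: r, high by f(r − s)

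Example with N = 150, f = 20%, r = 75%, s = 10%: 30 children are unscored and 120 scored. Responders are 0.75 × 120 = 90 among the scored and 0.10 × 30 = 3 among the unscored. The three rates are 93/150 = 62%, 90/150 = 60% and 90/120 = 75%.

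Ranges for f = 10-30%, r = 70-80%, s = 0-30%:

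- Non-responder rule: low by 0 to 0.30 × 0.30 = 9 points.
- Dropping: high by 0.10 × (0.70 − 0.30) = 4 points to 0.30 × (0.80 − 0) = 24 points.

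**The case against.** **The lost score depends on the clock chosen.** This stands. Every sentence that defines response leaves the dose unnamed, and on the last-dose reading each re-dosed child has a scheduled score. That reading changes the endpoint, as step 2 shows, so it moves the problem without removing it.

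**Some score will exist when re-dosing is decided.** Largely fair. The Protocol Outline makes a score the re-dosing criterion, times are approximate and actual times are recorded. A decision score taken at 11-14 min would lie inside a ±4 min window. A reader might infer from the table that these children will have nothing near 15 min; the documents do not go that far. But the scheduled 10-min score can support the decision by itself, and no text calls for another.

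**The separate SAP may settle it.** Section 7 defers detail to a SAP that is not in the material reviewed. It could name the clock and the missing-score rule. It could not supply an uncollected score.

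**The consequence is limited.** This also stands. Section 7.4 makes all analyses descriptive, no test depends on this rate, and 7.4.1 specifies a 95% confidence interval only for the within-30-min proportion. It is the reason for a moderate rating.

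**Conclusion.** The contradiction is real and rests on the text alone: 4.3.2 and 6.1.1 start the clock at different doses, and the endpoint definitions do not choose. At nominal times, a second dose at 10-14 min either leaves no scheduled 15-min score (first-dose clock) or moves that score to 25-29 min after the first dose (last-dose clock). The gap is selective, since re-dosing is mainly for scores above 4.

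A reader might infer that the reported 15-min rate will be inflated, perhaps by as much as 24 points. The documents do not support that. The figure needs three assumed inputs at their extremes and also needs the unscored children to be dropped, whereas the FAS definition points to keeping them. If they are kept as non-responders there is no upward bias and the rate can only be low. FAS membership does not itself say that a missing score is a non-response, so the rule still has to be written. Nor can one infer that both primary endpoints fail: the within-30-min endpoint can be scored on either clock.

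Should fix.

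**What to change.** 1. Reconcile 4.3.2, Table 1 note b, 6.1.1 and 7.4.1 by naming one clock for both primary efficacy endpoints. The first dose is most consistent with 6.1.1.
2. On that clock, keep a pain score at 15 min after the first dose in re-dosed children, alongside the restarted schedule, and state the allowed window around 15 min. Specify that it is a pain score only, because 4.3.3 and 4.3.4 otherwise attach sedation and vital signs to each pain assessment.
3. State in 7.4.1 that all FAS children are in the denominator and that a child re-dosed for insufficient relief with no score in the window counts as a 15-min non-responder. Enter this in 7.3 as an explicit exception to its no-imputation rule.

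The cost is wording plus about one brief pain score per re-dosed child. That score comes shortly after the second dose, so it does not measure the first dose alone. The 15-min rate may look less favourable, and where the score is still missed the non-responder rule can understate it by f·s. The dosing rule is unchanged. For children already treated, only items 1 and 3 can still help.

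As a separate item, reconcile the sedation clock, which 4.3.3 ties to the second dose and 6.2.1 to the first.

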#### 4.3.3 Assessment of sedation

The level of sedation will be assessed using the University of Michigan Sedation Score (UMSS, [Appendix D](#)). The UMSS has been validated for the assessment of procedural sedation in children. Level of sedation will be assessed at baseline (i.e. pre-IMP administration) and at 10, 15, 20, 30, 45, and 60 min post IMP immediately following each pain assessment. If a second dose of IMP is needed the sedation score will be performed at the same time points relative to the second dose.

#### 4.3.4 Vital signs

The following vital signs will be measured at baseline and post IMP administration and recorded in the eCRF:

- Pulse rate (bpm): will be recorded from the pulse oximeter.
- Blood oxygen saturation (%), assessed by pulse oximetry (non-invasive method).
- Respiratory rate (breaths per minute).

The vital signs will be measured immediately after the pain and sedation assessments, at the same times points, i.e. at 10, 15, 20, 30, 45, and 60 min post IMP, or until additional analgesics or procedures needs to be initiated. If values are not within normal range after 1-hour, vital sign measurements can be continued until ED discharge or until additional procedures need to be initiated.

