- c) IMP will be administered to the participant while sitting in an upright position using the appropriate strength depending on the participant's weight. See more info in the IMP section and in the IMP manual.
- d) Adverse events will be collected spontaneously at all visits using open questioning.
- e) Nasal tolerability and irritation will be assessed using combined participant reported symptoms and investigator examination/inspection of the nasal cavities. Nasal tolerability will be performed twice; appr 30 min and 60 min after the *last* IMP administration (following pain, sedation and vital signs assessments).
- f) Treatment satisfaction will be addressed by asking the standardized questions "*How satisfied are you with the study drug that you/your child received? Please think about how it helped their pain, how it was given, any side effects, and how quickly you/your child recovered*". Respondents will answer using a 5-point Likert scale (very unsatisfied, unsatisfied, neutral, satisfied, very satisfied). Feasibility (i.e. acceptance of nasal administration) will be addressed by the healthcare staff asking the child: *If you were in this situation again*

and needed pain medication, would you like to receive the nasal spray? If not possible by the child, the parent/legal guardian will assess nasal acceptability.

g) Any medication given for AEs during the time from enrolment to follow up should be entered in the eCRF. Any 'rescue medication' (described as additional analgesics due to insufficient effect of IMP during the 60 min after the last dose of IMP), should be entered in the eCRF. The time given should also be noted.

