### 6.2 Assessment of safety and tolerability

#### 6.2.1 Primary safety and tolerability variables

To investigate the safety and tolerability of IN CT001 in pediatric participants in the acute care setting experiencing pain of moderate or severe intensity.

- Sedation as assessed by sedation score on the University of Michigan Sedation Scale (UMSS) (Malviya et al, Anesthesiology 2004) at the following timepoints: baseline and 10, 15, 20, 30, 45 and 60 min after first IMP administration. If a second IMP dose is needed, sedation will be performed at the timepoints relative to first IMP administration.
- Respiratory depression, assessed by respiratory rate.
- Peripheral Oxygen saturation, as assessed by peripheral oximetry.
- Cardiovascular stability, as assessed by pulse rate.
- Number of reported Adverse Events, graded by intensity and severity.
- Number of AEs reported per participant.
- Local nasal irritation as assessed by combined participant and investigator feedback at 30 and 60 min post IMP administration.

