## Appendix D

### Michigan University Sedation Scale

#### University of Michigan Sedation Scale (UMSS)

---

0	Awake and alert
1	Minimally sedated: tired/sleepy, appropriate response to verbal conversation and/or sound
2	Moderately sedated: somnolent/sleeping, easily aroused with light tactile stimulation or a simple verbal command
3	Deeply sedated: deep sleep, arousable only with significant physical stimulation
4	Unarousable

S. Malviya\* , T. Voepel-Lewis, A. R. Tait, S. Merkel, K. Tremper and N. Naughton. Depth of sedation in children undergoing computed tomography: validity and reliability of the University of Michigan Sedation Scale (UMSS) British Journal of Anaesthesia 88 (2): 241±5 (2002)

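### In children drowsy enough to need rousing, respiratory rate is counted just after the pain and sedation scores and could understate drug-induced depression

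*Combined protocol and SAP*

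**What the plan says.** The order of assessments at each post-dose timepoint is explicit, and the protocol states it consistently.

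- Section 4.3.3 schedules the UMSS at 10, 15, 20, 30, 45 and 60 "min post IMP immediately following each pain assessment". Table 1 note a agrees: "Sedation will be assessed immediately after pain intensity assessments using the UMMS score".
- Section 4.3.4 then places pulse, SpO2 and respiratory rate: "The vital signs will be measured immediately after the pain and sedation assessments, at the same times points". The times it goes on to list are the six post-dose ones.
- Table 1 note e and section 4.3.5 put nasal inspection last, "following pain, sedation and vital signs assessments".

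Section 6.2.1 lists among the primary safety and tolerability variables: "Respiratory depression, assessed by respiratory rate". SpO2 and pulse rate are in the same list. Section 7.4.1 summarises measured values and changes from baseline for all three at each timepoint, by age group and overall.

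Appendix D defines UMSS level 2 as a sleepy or sleeping child who is "easily aroused with light tactile stimulation or a simple verbal command", and level 3 as "Deeply sedated: deep sleep, arousable only with significant physical stimulation". Under section 4.3.2, children aged 9 and over state their own NRS number. Section 7.4.1 describes Wong-Baker as self-reported too. FLACC, at ages 1 to under 5, is scored by the investigator.

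**The concern.** Drug-induced respiratory depression is of most interest in a child who has become drowsy. On this schedule that child is asked for a pain score (from age 5), then roused as far as needed to fix the UMSS level, and only then has breaths counted. If rousing speeds up breathing, the recorded rate reflects a stimulated child and not the resting state.

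Respiratory rate is the stated measure of respiratory depression, and the protocol's rationale (section 1.6) claims a reduced risk of exactly that. There is no control arm measured in the same order against which the readings could be judged. The safety report could then present respiratory rates that look more reassuring, in the few children who matter most, than an undisturbed count would have shown.

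**Working it through.** The plan states no figure on this point, so there is none to reproduce. The check sets the sections side by side.

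**1. How many readings follow this order?** Six scheduled post-dose sets (10, 15, 20, 30, 45 and 60 min), and the order applies to all 6. This counts readings taken in that order, not readings distorted by it.

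**2. Which children are stimulated by the scoring?**
- UMSS 0 is an alert child, who needs no added stimulus.
- UMSS 1 is scored on response to conversation or sound, so any disturbance is slight.
- UMSS 2 and 3 are defined by response to voice or light touch, and to significant physical stimulation. Telling them apart, or telling 3 from 4, means applying the stimulus.
- NRS and Wong-Baker add a verbal exchange at ages 5 and over. FLACC is mainly observation, though its consolability item refers to response to touch or talk. UMSS follows at all ages.

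The plausible reach is therefore children at about UMSS 2 or above.

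**3. Does anything in the plan supply an undisturbed reading?** No section asks for a respiratory count before scoring. None makes continuous oximetry or respiratory recording study data. None gives a numerical definition of respiratory depression.

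**4. Does change from baseline remove the effect?** Not reliably.
- Section 4.2 (Part 2) and the Table 1 asterisk allow baseline vital signs to come from routine triage, so they need not follow the same sequence.
- A baseline taken in the study is from a child in moderate or severe pain (section 3.1). Pain itself may raise respiratory rate, so relief alone could produce a fall. That works against the rousing effect.

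The net direction for the change score cannot be settled from the documents.

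**5. Illustration on assumed values only.** Let *q* be the true proportion of children with respiratory depression, on whatever definition is adopted, and *m* the fraction of those cases hidden by the order. With 150 children, the expected number recorded is 150 × *q* × (1 − *m*), and the chance of recording none is (1 − *q*(1 − *m*))^150.

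| Assumed *q* | *m* = 0 | *m* = 0.25 | *m* = 0.50 | *m* = 0.75 |
|---|---|---|---|---|
| 1%: expected cases; chance of none | 1.5; 22.1% | 1.125; 32.3% | 0.75; 47.1% | 0.375; 68.7% |
| 2%: expected cases; chance of none | 3; 4.8% | 2.25; 10.4% | 1.5; 22.1% | 0.75; 47.1% |
| 5%: expected cases; chance of none | 7.5; 0.05% | 5.625; 0.3% | 3.75; 2.2% | 1.875; 15.2% |

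Worked cell: *q* = 2%, *m* = 0.50 gives (1 − 0.01)^150 = 0.221. Neither *q* nor *m* is in the documents. The table shows only that, when cases are rare, hiding a few changes what a study of 150 can report. It is not evidence that any are hidden.

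**The case against.** The case against is substantial, and much of it stands.

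- **No effect size.** Nothing in the documents says that scoring raises respiratory rate, or by how much. That rousing stimulates breathing is ordinary clinical reasoning. This stands: it supports a likely direction for the raw count in drowsy children, and nothing quantitative.
- **Few children may be affected.** Section 1.4.2 reports minimal sedation and stable heart rate and saturation in earlier experience, although redaction hides the setting. This also stands. A reader might infer from the fixed order that every post-dose set is distorted; Appendix D does not support that for alert or minimally sedated children.
- **The net bias may not be toward reassurance.** A reader might infer that the order tilts the whole study toward finding no respiratory depression. The documents do not support that, because a painful baseline pulls the change score the other way and triage baselines have an unknown sequence.
- **Other routes catch events.** Clinically significant abnormal vital signs and signs seen by staff count as adverse events (sections 6.3 and 6.3.2), and a physician is present at dosing (section 1.7.1). The outline's primary safety endpoints are adverse-event counts, with vital signs listed only as assessments. This limits the consequence but does not correct the scheduled reading, which section 6.2.1 does list as a primary variable.
- **Reversing the order could harm the pain score.** The 15-min pain score is a primary efficacy endpoint, and handling a child aged 1 to 4 before FLACC could raise the score for crying or activity. This is a fair objection to a hands-on reversal. It is largely met if the count is by observation and the probe is already on.

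**Conclusion.** The point holds in a limited form. As written, the plan records respiratory rate in children at about UMSS 2 or above just after they have been stimulated, and nothing elsewhere supplies an undisturbed count. The rate could understate drug-induced depression in those children; the effect on SpO2 is probably smaller.

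The size is unknown. The conclusion rests on one assumption from outside the documents, that rousing a drowsy child raises respiratory rate. The vital-sign analysis is descriptive, so no test or decision rule changes, and the plan can be carried out as it stands. It is still worth correcting, because the weakness falls on the plan's own measure of respiratory depression and can be avoided at little cost.

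**What to change.** Reword sections 4.3.3 and 4.3.4, Table 1 note a, and the matching order in section 4.3.5 and Table 1 note e, so that each timepoint runs as follows:

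1. Count respiratory rate by observation, without touching or speaking to the child.
2. Read SpO2 and pulse from an oximeter probe already in place.
3. Take the pain score.
4. Score the UMSS.
5. Inspect the nose last, at 30 and 60 min, as now.

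Use the same order for baseline readings taken in the study. Flag baseline vital signs carried over from triage, so that changes from baseline can also be summarised without them.

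The cost is protocol and worksheet wording, with the same staff, equipment and timepoints, provided the probe can stay on between readings; the documents neither require nor rule this out. The pain score, including the 15-min primary efficacy score, falls slightly later (about a minute, assumed). Section 4.2 already treats the pain times as approximate and has the actual times recorded. If children have already been treated under the present order, record which order applied to each child.
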